6.3.6 End of Study and Follow Up

Final study visit at 12-Months (post randomization): Patients will complete the self-report measures and have their chart review completed. Patients in the MJS group will also complete measures regarding perceived use, ease of use and use behavior. Patients will also complete an exit interview where they will be queried about their experiences using the MJS tool over the past 12 months and recommendations for improvements. The visit will be conducted either via telephone with a RA or REDCap, depending on the patient's preference. This visit will take approximately one hour.

In addition, providers will be asked to complete measures regarding perceived use, ease of use, use behavior and physician communication at 12 months. Providers will also complete an exit interview where they will be queried about their experiences using the MJS-EHR interface over the past 12 months and recommendations for improvements. The ECR tool

interface over the past 12 months and recommendations for improvements. The PCP study visit will take approximately 30 minutes.

6.4.2 Sample Size Considerations

Formative phase: Sample size estimates for this phase are based on best practices for maximizing information power of qualitative research. Information power is determined by the specificity of the study aims, use of theory, and dialogue quality. It is recommended to begin with 4-8 participants and add to the sample, as needed to maximize information power.

Clinical Efficacy Phase: Power calculations are based on comparable studies using mHealth solutions to improve clinical and patient-reported outcomes in patients with T2D. We expect a group difference of 0.6%-1.4% between MJS DIABETES and UC groups at month 12 as suggested in Baron et al. This study compared the effects of a mHealth intervention on HbA1c and PROs including health-related quality of life and depression among a sample of 81 patients with T2D. Based on this study, we assume that a SD of HbA1c is 1.6%. Using a two-sample t test, for 80% power and 5% type I error, we can detect a 0.6% group difference with n=113 per group. With that same sample size, we are able to detect a 0.3% reduction in HbA1c for the MJS DIABETES group at month 12 compared to baseline. An attrition rate of 20% will ensure that 282 patients (141 per group) complete the study and

Study Number s18-01044

March 17, 2020 - version 9

have adequate data. This attrition rate is comparable to other clinic-based T2D trials in vulnerable populations.

6.4.3.1 Primary Analyses

Our analytic plan to achieve our outcomes at each phase is as follows:

For the formative phase, focus groups will be transcribed (and translated in English) verbatim and coded using Atlas.ti. The analysis of the qualitative data from patient and PCP focus groups will be done in two parts: 1) A brief report of the predominant themes for immediate use in the design workshop, described below, and 2) content analysis of the sessions to be shared in future publications in order to advance the science on the use of PROs for diabetes management in primary care practices.

For the brief report, [name] and a trained RA will conduct a debriefing meeting after each focus group to create a summary that outlines the key barriers, facilitators, needs and workflow preferences among patients and PCPs. After completing all 3 focus groups, the RA will calculate the mean importance ratings for each of the PROs discussed by the patients and PCPs. The study team will use the mean scores in concert with recommendations for selection of PROs in diabetes research outlined by Reaney et al. to identify the appropriate PROs that will be collected in the clinical efficacy trial. The brief report will drive the development of workshop materials and exercises (draft MJS content, workflow maps), as described below.

For the content analysis, session transcripts will be analyzed by [name] and

consultant, [name], [who are experienced in qualitative research], using the constant comparison method. Specifically, the coders will independently review the transcribed focus groups to identify themes related to the design of the MJS intervention for English and Spanish-speaking patients, and PCPs, and barriers and facilitators to uptake. The coders will iteratively develop a codebook during this process to maintain coding consistency and transparency in coding decisions. Discrepancies in coding will be resolved through an interactive process of re-reading and discussing the transcripts until consensus is reached; the codebook will be updated to reflect any changes. Assessments of inter-rater agreement will be calculated using Krippendorff's alpha to ensure an acceptable level of agreement is reached (>0.80) between the coders. To evaluate the usability of MJS DIABETES, we will follow best practices for instant data analysis (IDA) of usability data. After each session, the study team will meet to brainstorm the usability and workflow issues (e.g., content, readability, navigation, alerting and visualizations) that were observed. Each identified issue will be then categorized as either: critical (unable to complete the task), severe (significant delay or frustration in task completion), or cosmetic (minor issue). Each of these issues will be mapped onto the transcribed audio and screenshots captured during the sessions to provide specific and detailed recommendations for refinement of the MJS mobile platform and EHR interface before proceeding to the next testing session. After completing all of the sessions, we will conduct affinity mapping to identify the major issues that were causing critical and severe errors in the testing sessions. This inductive process involves aggregating the separate issues identified in the brainstorming sessions into larger themes related to usability and workflow of MJS DIABTES. This creates a more synthesized and

comprehensive understanding of the most severe and frequent issues that must be addressed before testing MJS DIABETES in the RCT. Previous research have shown that using IDA can reduce the amount of time needed for analysis by 90%, while achieving 85% overlap in identifying critical usability issues compared to traditional qualitative analytic methods. The primary output of this step is the fully functional, well-integrated MJS DIABETES intervention for testing in the clinical efficacy trial.

For the clinical efficacy phase, the primary analysis is intent-to-treat (ITT). For the ITT approach, all patients that are randomly assigned to the intervention or UC groups will be included in the analysis, regardless of program and evaluation compliance. The primary outcome is the mean reduction, compared to baseline, in HbA1c at 12 months in the MJS diabetes intervention vs. UC arm. HbA1c will be treated as a continuous variable in this analysis. We will test the treatment X time interaction in a random effects linear regression model to test the time-specific differences in HbA1c at 12 months attributable to the intervention. We also will use the "lincom" command in Stata to estimate differences in time-specific changes from baseline. In additional analyses, we will adjust for covariates (e.g., ethnicity, gender, age, income, education, employment, insurance) unbalanced between the treatment arms at baseline at $p=0.10$.

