6.1.2 Method of Assignment/Randomization

This project has a hierarchical study design with each patient nested within a PCP thus, randomization will occur within PCP. The study statistician ([name]) will oversee randomization, which will be carried out using a SAS macro after completion of the consent procedures and baseline data collection. Patients will be randomly allocated to either the intervention (MJS DIABETES) or UC at a 1:1 ratio. A random number from 0 to 1 will be used to determine to which group the subject is assigned. The standard cut score will be set at 0.5 for the first n subjects from the same PCP. Those who receive a random number between 0 and 0.5 will be assigned to the UC group and those with a random number greater than 0.5 will be assigned to the MJS group. The balance between the groups within each PCP will be carefully weighted after the total number of subjects from a PCP reaches a number greater than n. Before the randomization procedure, the number of subjects randomized to each arm of the study for each PCP will be estimated using SAS macro programs. If more than the n subjects are randomized initially, the cut score for the next subject is equal to the ratio of the experimental arm (n1) to the subjects already randomized

(m) for that PCP (n1/m). The randomization log will be stored in a secure file, and will be password protected. Once a patient has met eligibility criteria and provided consent, the program manager will call the study statistician for the patient's group assignment. As is true for most behavioral interventions, the patient cannot be blinded to the group assignment. However, it is plausible that study staff could bias the study outcome by knowing the patient's group assignment. To mitigate the potential for this bias, the RA that is responsible for data collection will be blinded to the patients' group assignments and study hypotheses (i.e., single blind design).

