HbA1c	Average glucose levels over prior 3 months surrounding the study visit date	Electronic health record extraction Baseline, 3, 6, 9, 12

	Item/Scale	Assessment, 3, 6, 9, 12
Self-care behaviors	Summary of Diabetes Self-care Activities Measure ¹¹	Patient self-report Baseline, 3, 6, 9, 12
Covariates		
Demographics	Patient race/ethnicity, years in US, primary language, age, gender, household income, education level, marital status, employment status, health insurance PCP gender, race/ethnicity age, years of medical practice, years practicing at the FHC, and how well they know the patient (range: very well to not at all).	Patient and PCP Baseline
Characteristics of disease and medication regimen	T2D duration; target organ damage; medical comorbidities; #, class and doses of T2D medications other prescribed medications, Void Medication Adherence, PDC metric, Charlson Comorbidity Index	Electronic health record extraction Baseline, 12
Health care utilization	Healthcare Utilization questionnaire measures patient hospitalizations, clinic visits and emergency department use for T2D every 6 months during the course of the trial.	Patient self-report 6, 12
Theoretical Mediators		
Knowledge	Diabetes Knowledge Scale ¹²	Patient self-report Baseline, 3, 6, 9, 12
Self-efficacy	Diabetes Self-Efficacy Scale ¹³	Patient self-report Baseline, 3, 6, 9, 12
Outcome expectations	Outcome Expectations Questionnaire ¹⁴	Patient self-report Baseline, 3, 6, 9, 12
Patient-provider communication	Interpersonal Processes of Care survey-Short form ¹⁵	Patient self-report Baseline, 3, 6, 9, 12
Patient diabetes distress	Diabetes Distress Scale	Patient self-report Baseline, 3, 6, 9, 13
Process Measures		
Perceived usefulness	TAM3 survey ⁹	Patient and PCP self-report; 12 mos.
Perceived ease of use	TAM3 survey ⁹	Phase 1 live usability testing Patient and PCP self-report; 12 mos.
Relevance	TAM3 survey ⁹	Patient and PCP self-report; 12 mos.
Report Quality	TAM3 survey ⁹	Patient and PCP self-report; 12 mos.
Result Demonstrability	TAM3 survey ⁹	Patient and PCP self-report; 12 mos.
Communication	TAM3 survey ⁹	Patient and PCP self-report; 12 mos.
Behavior Intention	TAM3 survey ⁹	Patient and PCP self-report; 12 mos.
Provider Communication	Provider Communication survey	PCP Baseline and 12 mos.

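### The primary HbA1c model reads as an unconstrained change-from-baseline contrast with an open visit covariance and no PCP term: valid, but never more precise than a model with a common baseline

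*Combined protocol and SAP*

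**What the plan says.** Table 7 (section 6.1.3) schedules HbA1c at five times: "Electronic health record extraction Baseline, 3, 6, 9, 12". Section 6.4.3.1 defines the primary outcome as the mean reduction from baseline at 12 months, intervention against usual care. The model is given in one sentence: "We will test the treatment X time interaction in a random effects linear regression model". `lincom` is then used "to estimate differences in time-specific changes from baseline". The analysis is intention-to-treat: "all patients that are randomly assigned to the intervention or UC groups will be included in the analysis".

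The text does not name the random effects (patient intercept, patient slope, PCP), the coding of time, or the covariance across the five visits. Sections 6.4.3.2 and 6.4.5 refer to random effects without more detail. Section 6.1.2 describes "each patient nested within a PCP thus, randomization will occur within PCP", but no PCP term appears in any model.

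Covariates enter by three separate routes:
- Section 6.4.3.1: "In additional analyses, we will adjust for covariates", limited to those unbalanced at p=0.10. Section 6.4.3.2 likewise adjusts only if the arms are unbalanced.
- Section 6.1.3 says that the number, class and dose of diabetes medications will be a covariate. Table 7 lists further candidates under covariates: "T2D duration; target organ damage; medical comorbidities; #, class and doses of T2D medications". These are extracted at baseline and at 12 months.
- Section 6.4.5 adds whatever variables are found to predict missing data.

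**The concern.** Two things follow from the one-sentence model.

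First, a treatment-by-time model with differences in change from baseline normally gives each arm its own baseline mean and subtracts it. In a randomised trial the two baseline means differ only by chance. Estimating them separately adds noise that a common baseline mean, or adjustment for baseline HbA1c, would remove.

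Second, the standard error of the 12-month contrast depends on the covariance assumed across visits. Two competent analysts could fit different models from the same text, and one of those models can understate the standard error. Section 6.4.5 also relies on the random effects framework for unbiased estimates when data are missing at random. With the 20% attrition assumed in section 6.4.2, a likelihood analysis of incomplete data depends on that covariance too.

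**Working it through.** **The plan's own figure.** Section 6.4.2: difference 0.6, "we assume that a SD of HbA1c is 1.6" (percent), 80% power, 5% type I error, two-sample t test (two-sided assumed). The exact t calculation gives 113 per arm with power 0.801. Allowing for 20% attrition, 113/0.8 = 141.25, which agrees with 141 per group and 282 in total. The figure reproduces.

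**Precision formula.** Let s0 and s1 be the SDs at baseline and 12 months, ρ their correlation, and n the number per arm.
- Unconstrained change: variance = (2/n)(s0² + s1² − 2ρ·s0·s1).
- Common baseline: variance = (2/n)·s1²(1 − ρ²).
- The first bracket minus s1²(1 − ρ²) equals (s0 − ρ·s1)², which is never negative. With equal SDs the ratio is 2/(1 + ρ).

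A generalised least squares check on all five visits, with saturated means, complete data and known covariance, gives the same ratio. At ρ = 0.75 it is 1.143 whether correlation is flat or decaying.

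**Implied correlation.** Section 6.4.2 also states a detectable within-arm reduction of 0.3 with n = 113. It does not say which test was used. Read as a one-sample test of change at 80% power and two-sided 5%, it implies an SD of change of 1.1285. With SD 1.6 at both visits:
- ρ = 1 − 1.1285²/(2 × 1.6²) = 1 − 1.2735/5.12 = 0.751.
- Variance ratio = 2/1.751 = 1.142; CI width ratio = √1.142 = 1.069.
- Equivalent loss = (1 − 1/1.142) × 226 ≈ 28 of the 226 (2 × 113) analysed patients.
- If 0.3 is rounded from 0.25 to 0.35, ρ runs from 0.83 to 0.66 and the excess from 9% to 20%.

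**Sensitivity to baseline SD** (assumed, as the plan gives none). Hold the SD of change at 1.1285 and the 12-month SD at 1.6; ρ = (s0² + 1.6² − 1.1285²)/(2 × s0 × 1.6):

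| Baseline SD | ρ | Variance ratio | Patients lost of 226 |
|---|---|---|---|
| 1.2 | 0.710 | 1.003 | 1 |
| 1.4 | 0.725 | 1.048 | 10 |
| 1.6 | 0.751 | 1.142 | 28 |
| 1.8 | 0.786 | 1.301 | 52 |

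**Power for 0.6 at 113 per arm, equal SDs.** At ρ = 0.75: 98% (change) and 99% (common baseline). At an assumed ρ = 0.5: 80% and 90%, with 33% excess variance.

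**Covariance, illustration only.** Suppose a patient random intercept alone is fitted, variances are equal across visits, data are complete and the baseline-to-12-month correlation is 0.75. The model uses the mean of the 10 pairwise correlations in place of 0.75, so the ratio of model SE to true SE is √[(1 − mean ρ)/(1 − 0.75)]. The assumed correlations below are for gaps of 3, 6, 9 and 12 months; the number of pairs at each gap is 4, 3, 2 and 1.

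| Assumed correlations | Mean ρ | SE ratio | Type I error |
|---|---|---|---|
| 0.75 throughout | 0.750 | 1.000 | 5.0% |
| 0.80, 0.78, 0.77, 0.75 | 0.783 | 0.932 | 6.8% |
| 0.90, 0.85, 0.80, 0.75 | 0.850 | 0.775 | 12.9% |

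Type I error is 2[1 − Φ(1.96 × SE ratio)]. A simulation of 20,000 trials with 113 per arm gave 4.9%, 7.1% and 12.9%. A plain t test on 12-month change stayed at 4.8% to 5.2%.

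**The case against.** The strongest reply is that the planned contrast is valid and its power adequate, so the precision point is a preference of uncertain size. Much of this stands. The 14% needs both a paired-test reading and equal SDs. Section 6.4.2 does not say whether 1.6% is the SD of the level or of the change; if it is the change, the planned 80% power already covers the change contrast. Entry requires HbA1c above 7% on two visits, and baseline is drawn from a 6-month window against 90 days around the later visits. Either feature could lower the baseline SD, so a loss near zero is plausible.

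The unconstrained reading is also an inference. The fixed effects are not written out, and the same section speaks of differences at 12 months before it turns to change. It remains the ordinary reading of the text, and nothing in the plan constrains or adjusts for baseline HbA1c.

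A reader might infer that the plan has a 13% type I error. The documents do not support that. No section specifies an intercept-only model, the decay patterns are assumed, and flat correlation gives 5%. Nor does omitting PCP inflate error; that is neutral to slightly conservative. The common-baseline model does not retain more patients either, since the planned mixed model keeps them as well.

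Finally, it would be wrong to say that no covariate is fixed anywhere: section 6.1.3 commits to diabetes medications. The difficulty is that this commitment, the imbalance trigger and the missing-data route do not fit together.

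**Conclusion.** The point holds as a matter of efficiency and specification. The change contrast gives an unbiased comparison under randomisation, but it is never more precise than a common-baseline contrast when the covariance is correctly modelled. The best estimate from the plan's own figures is about 14% excess variance and a 7% wider interval. That is conditional on the paired-test and equal-SD readings, with a range of 0.3% to 30% over assumed baseline SDs of 1.2 to 1.8. A reader might go on to infer that the trial is underpowered; at the implied correlation, power for 0.6 is about 98% as planned, so the documents do not support that.

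The open covariance bears on error control only if an intercept-only model is chosen and correlation decays. The present text leaves that choice to the analyst. Naming PCP brings the model into line with the randomisation and repairs no demonstrated error. The amendment is worth making because it costs nothing in data, and confidence in the size of the gain is moderate.

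**What to change.** In section 6.4.3.1, specify a linear mixed model on HbA1c at baseline and months 3, 6, 9 and 12, with:
- visit as a categorical factor;
- baseline mean constrained equal across arms, and arm-by-visit terms from month 3;
- PCP as a stratification term;
- unstructured covariance across visits, with a pre-specified fallback if it does not converge;
- the month-12 arm difference as the single primary contrast. With a common baseline this equals the difference in mean reduction, so the primary outcome is unchanged and `lincom` still delivers it.

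Use the same form for the continuous self-care scores in section 6.4.3.2. It does not suit smoking, which section 6.1.3 scores as yes or no; that item needs its own model.

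Reconcile the three covariate routes in sections 6.1.3, 6.4.3.1/6.4.3.2 and 6.4.5 into one pre-specified list, using baseline values only. Section 6.1.3 wants medications to account for management during the study, but values recorded at 12 months are post-randomisation and may carry part of the intervention's effect. The plan should state this restriction openly as a change from that intention.

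Cost: SAP wording only, as every variable is already collected. The model spends about 13 degrees of freedom on 14 PCPs and 15 covariance parameters (5 × 6/2) on five visits, which is small against 282 patients.

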6.4.3.3 Safety/Pregnancy-related policy

Patients who are pregnant or planning to become pregnant in the next 12 months are excluded from this trial.

6.4.3.4 Analysis of Subject Characteristics

Baseline characteristics and outcomes will be summarized descriptively using mean values and standard deviation or frequency descriptions. During preliminary analysis, we will also examine: (1) comparability of treatment arms at baseline (based on Chi-squared statistics or t-tests, as appropriate) based on participant characteristics, (2) relationships between the response variables and potential covariates, and (3) predictors of missing data/drop-out. We will document any observed reasons for missing data during data collection.

6.4.3.5 Interim Analysis (if applicable)

Not applicable

6.4.3.6 Health economic evaluation

Not applicable

6.4.5 Handling of Missing Data

Univariate statistics and missing value analysis modules will be used to check the number and pattern of missing. We will use Little test to check the assumption of missing data completely at random (MCAR) or missing at random (MAR). Identified predictors of missing data will be included as covariates in a random effects framework, to provide unbiased

estimates of the intervention effect under an assumption of MAR (i.e., missingness depends on observed covariates but not on unobserved covariates). We will conduct sensitivity analyses to assess departures from this assumption.

7 - Trial Administration

7.1 Ethical Considerations

This study will be conducted in accordance with the ethical principles that have their origin in the Declaration of Helsinki.

To mitigate any breaches in security or privacy as it relates to the MJS DIABETES intervention, we will adhere to policies by the Federal Office of the National Coordinator for Health IT as well as the principles of the Markle Framework for Networked Personal Health Information and the technical specifications of the O-Auth protocol for user authentication. Based on these sources, the Privacy and Security Plan will include:

- Development of explicit policies governing the access to individual PRO data in the MJS intervention (e.g., limited to study staff who require it for authorized, legitimate, and documented purposes).
- A firm policy prohibiting the study staff or consultants (i.e., Rip Road, [name]) from access to individual patient health records, except for specific purposes of research approved by the IRB.
- Encryption of all sensitive user data within the MJS mobile platform and EHR interface to prevent unauthorized access and disclosure in the case of a physical loss. No PHI will be collected on the MJS platform.

- Regular training and reminders sent to study staff and consultants about system security and the need to follow related protocols to protect the confidentiality of user information. Policies will also be established for handling violations to security protocols, if they arise.
- A protocol outlining regular risk assessments and system audits to ensure a secure transmission of patients' data, including use of encryption protocols such as Secure Socket Layer (SSL) technology.

As part of their participation in this study, patients and providers will receive a small amount of payment to reimburse them for their time and effort. The payment is needed to reimburse patients and providers for the additional travel to the FHC/FGPs for study visits and additional time to participate.

